#### 5.4.2.1 Neurocognitive Events

Neurocognitive events will be identified and evaluated by routine safety monitoring of PE findings and AEs. Summarization of neurocognitive events will occur using pre-specified MedDRA terms and will be performed by SOC, severity, and relationship to study drug by previous treatment group in parent study and overall in OLE study.

Confidential

Page 17 of 27

Page 119 of 129

#### 5.4.3 Clinical Cardiovascular Endpoints

Clinical cardiovascular endpoints will be monitored and adjudicated by an independent blinded expert CEC for this study and other ongoing studies the ETC-1002 program. Adjudicated clinical endpoints that are treatment-emergent will be summarized by event type and previous treatment group in parent study and overall in OLE study. All events will be provided in a listing. Additional details regarding clinical endpoints and clinical endpoint definitions will be included in CEC charter.

#### **5.4.4 Laboratory Evaluations**

Continuous laboratory parameters (serum chemistry, hematology, coagulation (only for those patients receiving anti-coagulation), urinalysis, urinalysis [microscopic]) listed in Table 4 will be summarized in conventional unit and SI unit using descriptive statistics at each scheduled visit starting from the baseline of the parent study. The similar completer analysis set approach for efficacy analysis described in section 5.3 will be used for selected parameters. Missing values for any of the laboratory evaluations will not be imputed; that is, only observed case data will be used.

Fasting serum glucose and HbA1c will be summarized using descriptive statistics for the observed value, change from baseline, and percent change from baseline at each scheduled visit by history of diabetics.

Categorical urinalysis data will be listed, but will not be summarized.

As part of the AESI evaluation, below safety lab abnormality will be summarized by treatment group. All post-baseline lab values during the on-treatment period are being considered. Further details are provided in Section 5.4.6.1 through 5.4.6.4.

- ALT or AST (>  $3 \times$  Upper limit of normal (ULN) and > $5 \times$  ULN)
- Total bilirubin (TB) (> 2 × ULN)
- Potential Hy's Law case: (ALT and/or AST > 3 × ULN with concurrent TB > 2 × ULN)
- CK (>  $5 \times$  ULN) and (> $10 \times$  ULN)
- Fasting Serum Glucose (mg/dL) ( $\leq$  50, and  $\geq$  126) by history of diabetics
- HbA1C ( $\geq$  6.5%) by history of diabetics
- Creatinine (change from baseline for >1 mg/dL)
- eGFR (< 15 mL/min/1.73m^2, 15 29 mL/min/1.73m^2)
- Hgb (g/dL) (decrease from baseline for  $\geq 2$  g/dL)
- Hgb (< 8 g/dL)

The number and percentage of patients with the following laboratory abnormalities will be summarized by the parent study baseline statin intensity, previous treatment group in the parent study, and overall in the OLE study:

#### Confidential

Page 18 of 27

- ALT or AST (>  $3 \times$  ULN and > $5 \times$  ULN)
- TB (>  $2 \times ULN$ )
- Potential Hy's Law case: (ALT and/or AST >  $3 \times$  ULN with concurrent TB >  $2 \times$  ULN)
- CK (>  $5 \times ULN$ ) and (> $10 \times ULN$ )
- Creatinine (change from baseline for > 1 mg/dL)
- eGFR (< 15 mL/min/1.73m^2, 15 29 mL/min/1.73m^2)
- Hgb (g/dL) (decrease from baseline for  $\geq 2$  g/dL)
- Hgb (< 8 g/dL)

For labs of interest (such as uric acid, hemoglobin, creatinine, BUN, and Fasting glucose by diabetes history), a line plot will be generated to visualize the mean values over time.

A matrix display of liver dysfunction shift from baseline to maximum value will be used to visualize the abnormal values of labs including AST, ALK-P ALT, and TB.

Table 2:	Clinical Laboratory Parameters (Safety)
----------	---

Clinical Laboratory Test	Clinical Laboratory Test
• Hematology	Blood Chemistry (serum, fasting)
• Hematocrit (Hct)	• Albumin (Alb)
• Hemoglobin (Hgb)	• Alkaline phosphatase (ALK-P)
• Mean corpuscular hemoglobin (MCH)	• Alanine aminotransferase (ALT; SGPT)
• Mean corpuscular hemoglobin	• Aspartate aminotransferase (AST;
concentration (MCHC)	SGOT)
• Mean corpuscular volume (MCV)	• Blood urea nitrogen (BUN)
• Platelet count	• Calcium (Ca)
• Red blood (RBC) cell count	• Carbon dioxide (CO2)
• White blood (WBC) cell count with	• Chloride (Cl)
differential (absolute and %)	• Creatinine
Urinalysis (Dipstick)	• Creatine kinase (CK)
• Clarity	• Glucose
Bilirubin	• Lactate dehydrogenase (LDH)
• Color	Phosphorus
• Glucose	• Potassium (K)
• Ketones	• Sodium (Na)
• Leukocyte esterase	• Total and direct bilirubin (TB)a
• Nitrate	• Total protein
Occult blood	• Uric acid
• pH	Coagulation—only in patients receiving
• Protein	anticoagulant therapy that in the investigator's
• Specific gravity	judgment require monitoring at Month 0 and
• Urobilinogen	3 to 5 days post-Month 0
-	Prothrombin time
	• International normalized ration (INR)
Urinalysis (Microscopic)-only if urine dipstick	Other Labs:
abnormal	• Urine pregnancy test
• Bacteria	• Hemoglobin A 1C (HbA 1C )
• Casts	
Crystals	
• Epithelial cells	
• RBC	
• WBC	

 $^{\rm a}\,$  If TB  ${\geq}1.2 \times$  ULN, a reflex indirect (unconjugated) bilirubin will be obtained.

#### Confidential

The number and percentage of patients with laboratory abnormalities (i.e., laboratory values outside the stated laboratory normal range) will be summarized at each time point (i.e., including baseline and post-baseline time points) for each laboratory parameter. The determination of laboratory abnormalities will take into account any unscheduled laboratory assessments. Additional lab-related summaries will be provided as follows for hepatic safety, musculoskeletal safety, diabetes and glycemia, and renal safety.

#### 5.4.4.1 Hepatic Safety

For liver-associated enzymes and total bilirubin (TB), the number and percent of patients with abnormal values for ALT (>3 × ULN, > 5 × ULN), AST (> 3 × ULN, > 5 × ULN), and TB (> 2×ULN) will be summarized by overall, normal baseline ALT/AST/TB and abnormal baseline ALT/AST/TB.

Hy's law criteria (>  $3 \times$  upper limit of normal [ULN] for either ALT or AST, with accompanying TB >  $2 \times$  ULN) will also be applied to the data; any potential Hy's law cases will be listed separately. In the case of patients with Gilbert's disease, TB will be fractionated and the determination of  $2 \times$  ULN will be based upon direct (conjugated) bilirubin.

The number and percentage of patients experiencing a single incident or confirmed and repeated incidence of abnormal liver function test values for ALT (>3 × ULN, >5 × ULN), AST (>3 × ULN, >5 x ULN), CK (>5 × ULN, >10 × ULN) and either ALT and/or AST (>3 × ULN, >5 × ULN) will be summarized by the previous treatment group in the parent study and overall in the OLE study. A single incident is defined as the patient experiencing only one abnormal incident of the liver function test value. Repeated and confirmed incidence is defined as the patient experiencing at least one of the following: the last on-study liver function test value is abnormal, the last on-treatment liver function test value is abnormal liver function test value is followed by another abnormal liver function test value for the same test.

A separate listing for direct bilirubin will be provided for those who have Gilbert's syndrome.

#### 5.4.4.2 Musculoskeletal Safety

CK levels will be summarized by the value and change from baseline in the value, by treatment group and visit as well as baseline eGFR category. In addition, the number and percent of patients with abnormal CK values (>5 X ULN, >10 × ULN) will be summarized. These summaries of patients with abnormal CK will be performed overall, normal baseline CK, and abnormal baseline CK.

#### 5.4.4.3 Diabetes and Glycemia

For fasting glucose and HbA1C (%), a shift table from baseline with the number and percent of patients will be categorized as below:

Fasting glucose: >= 126 mg/dL; 100-125 mg/dL, and < 100 mg/dL; Confidential Page 21 of 27

Page 123 of 129

Version 1.3, Dec 04, 2019 Statistical Analysis Plan

HbA1C (%): >=6.5%; >5.5 to <=6.4% and <=5.5%.

These tables will be summarized by history of Diabetes.

Descriptive summary for fasting serum glucose and HbA1C will be provided by history of diabetics, previous treatment group in parent study and overall at each scheduled visit.

#### 5.4.4.4 Renal Safety

Shift tables of eGFR category from baseline over the study, will be provided by previous treatment group in parent study and overall.

In addition, renal function abnormality will be identified as: (1) A creatinine change from baseline of > 1 mg/dL (2) eGFR value  $<30 \text{ mL/min/}1.73\text{m}^2$ . A shift table from baseline with the number and percent of patients using the two categories will be presented.

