10.1.4.3.2. Monitoring and Management of Elevated Serum Creatinine

If at any time after randomization, a patient experiences a decrease in estimated glomerular filtration rate (eGFR) to the level of 15 mL/min/1.73 m²) or if the patient experiences acute renal failure, the patient should be withdrawn from IMP treatment but will be asked to continue to be followed for safety using the protocol-specified visit schedule (see Appendix 1)

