12.6. Other Safety Endpoints

Laboratory Results

Actual value or change from baseline (where appropriate) in clinical safety laboratories, including hematology, blood chemistry, HbA_{1C}, glucose, and urinalysis will be summarized at each scheduled visit.

Shift tables for selected safety laboratory parameters will be provided.

Physical Measurements

Height and weight will be summarized at each scheduled visit.

Vital Signs

Hear rate, SBP and DBP will be summarized at each scheduled visit.

Hepatic Safety

Actual value and change from baseline in liver-associated enzymes and TB will be summarized at each visit. In addition, the number and percent of patients with normal vs. abnormal values for ALT, AST, and TB will be summarized by their baseline and postbaseline status. Hy's law criteria (>3 × ULN for either ALT or AST, with accompanying TB >2 × ULN or patient's baseline) will also be applied to the data; any potential Hy's law cases will be listed separately. In the case of patients with Gilbert's disease, TB will be fractionated and the determination of $2 \times ULN$ based upon direct (conjugated) bilirubin. For patients with Gilbert's Disease $2 \times$ the conjugated bilirubin will be used as the criterion.

Musculoskeletal Safety

Adverse events of muscle-related symptoms will be summarized. Creatine kinase levels will be summarized by the value and change from baseline in the value, by visit. In addition, the number and percent of patients with normal vs. abnormal CK values will be summarized by their baseline and post-baseline status.

Diabetes and Hyperglycemia

Cases of new onset of diabetes will be recorded as AEs and will be summarized using the appropriate SOC. These events will be summarized by severity and relationship to study drug. Glucose and HbA_{1C} will be monitored at baseline and at Weeks 12, 52 and 78, and be summarized by history of diabetes.

Renal Safety

Baseline eGFR will be summarized for actual value and for baseline eGFR categories. Shift tables of eGFR category from baseline over the study, will be provided. Shift tables of urine protein (negative/positive) from baseline over the study, will be provided. Values of CK will be summarized by baseline eGFR category.

Neurocognitive Events

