#### **5.2.4 Demographic and Baseline Characteristics**

Two sets of baseline values will be defined: baseline of parent study and OLE study. The parent study baseline will be taken directly from the parent study, and the OLE baseline is defined as last non-missing value prior to the first dose of IMP in the OLE study. The following demographic and both baseline characteristics will be summarized using descriptive statistics by previous treatment group in parent study, as well as overall, for safety population:

- Age group (18-40, 41-64, 65-74, and >=75 years), gender, race, ethnicity, region (North America, and Europe), height (cm), weight (kg), body mass index (BMI) (kg/m^2) (< 25, 25 - < 30, ≥ 30 kg/ m^2), systolic and diastolic blood pressure, fasting lipid parameters (TC, LDL-C, HDL-C, non-HDL-C, and TG), apoB, and hs-CRP.
- Cardiovascular risk factors from the parent study: ASCVD (Yes/No), HeFH (Yes/No), baseline statin intensity (derived) (low or moderate, high), eGFR category, tobacco history, alcohol history, history of diabetics, and history of hypertension.
- The baseline estimated glomerular filtration rate (eGFR) categories are: normal: ≥90 mL/min/1.73m^2; mild Renal Impairment: 60-89 mL/min/1.73m^2; moderate Renal Impairment: 30-59 mL/min/1.73m^2, and severe Renal Impairment (15-29 mL/min/1.73m^2).

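### SAP v1.3 renal safety leaves out the protocol's urine-protein shift table, orders a baseline shift on a criterion that is already a change from baseline, and gives the eGFR shift table no class below 15

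*SAP*

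**What the plan says.** **Two shift tables in SAP v1.3, 5.4.4.4.** The first is by eGFR class: "Shift tables of eGFR category from baseline over the study, will be provided by previous treatment group in parent study and overall". The second rests on two abnormality criteria, "A creatinine change from baseline of > 1 mg/dL" and an eGFR under 30 mL/min/1.73 m², after which the section states: "A shift table from baseline with the number and percent of patients using the two categories will be presented". It does not say which baseline applies, although 5.1 defines two (parent study and OLE).

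**eGFR classes.** The only set in v1.3 is in 5.2.4, introduced by "The baseline estimated glomerular filtration rate (eGFR) categories are: normal" (90 and above), followed by 60–89, 30–59 and, lowest, "severe Renal Impairment (15-29" mL/min/1.73 m²). Elsewhere v1.3 does go lower. The laboratory-abnormality list in 5.4.4 counts on-treatment eGFR below 15 and 15–29, and also creatinine rises above 1 mg/dL. Both are repeated by parent-study statin intensity. Protocol 10.1.4.3.2 has a rule triggered by "a decrease in estimated glomerular filtration rate (eGFR) to the level of 15" mL/min/1.73 m².

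**Urine protein.** Protocol 12.6, under Renal Safety, states: "Shift tables of urine protein (negative/positive) from baseline over the study, will be provided". SAP v1.3, 5.4.4.4 does not mention urine protein, and 5.4.4 states: "Categorical urinalysis data will be listed, but will not be summarized". Later, 5.4.4 also asks for out-of-range counts at every time point for every laboratory parameter, and its Table 2 includes dipstick protein. Section 2 gives the SAP precedence over the protocol. Section 4.6 reports no departure from the protocol's planned analyses.

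**The concern.** Safety is the primary objective, Renal Safety is a listed safety endpoint in v1.3, and renal disorders form an AESI group in its Appendix 2. With one open-label arm and no inference planned, within-patient movement from baseline is a main way to read renal change.

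On that reading the specification has three weaknesses. One table uses a criterion that cannot be true at the table's own starting point. Another has no stated place for the lowest eGFR values. A third table, promised in the protocol, is not carried into the document that governs the final analysis, and the section meant to declare such changes says there are none. A programmer would have to guess at the first two and could properly leave out the third.

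**Working it through.** The plan gives no figure to reproduce. The check applies the written definitions and compares the texts.

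**1. Creatinine criterion.** Let b be the baseline creatinine. The change evaluated at that baseline is b − b = 0. For b = 0.6, 1.0, 1.8 and 3.0 mg/dL the change is 0 each time, and 0 > 1 is false. The abnormal-at-baseline row is therefore empty by construction. This holds for a parent-to-parent or an OLE-to-OLE table. It need not hold if the shift starts at the OLE baseline while the change is measured from the parent baseline.

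**2. Are the two criteria levels of one table?**

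| Creatinine change (mg/dL) | eGFR | Rise > 1 | eGFR < 30 |
|---|---|---|---|
| 1.5 | 25 | yes | yes |
| 0.2 | 25 | no | yes |
| 1.5 | 40 | yes | no |
| 0.2 | 70 | no | no |

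A patient can meet both, either or neither, so these are two separate yes/no flags. The history suggests why they are called categories. In SAP v1.0 (5.4.5.4) the pair was one abnormal state, combining both criteria, and its intended opposite. From v1.1 the opposite was dropped and the two criteria were numbered (1) and (2), but the sentence about two categories stayed. In v1.1 it named both baselines; in v1.2 and v1.3 it names neither.

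**3. eGFR classes.** Applying 5.2.4 to whole numbers from 0 to 120 leaves 0 to 14 unclassified and everything from 15 upward classified. If eGFR is not rounded, values such as 29.5, 59.5 and 89.5 also fall between classes.

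**4. Urine-protein shift, document by document.**

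| Document | Urine-protein shift specified |
|---|---|
| Protocol 12.6 (Amendment 2) | yes |
| SAP v1.0, 5.4.5.4 | yes |
| SAP v1.1, 5.4.5.4 | no |
| SAP v1.2, 5.4.5.4 | no |
| Day 120 addendum | yes (Tables 14.3.6.3.1 and 14.3.6.3.2) |
| SAP v1.3, 5.4.4.4 | no |

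Amendment 2 edited this very paragraph of 12.6. It removed the sentence on muscle-related events and kept the one on urine protein. SAP v1.3 is written against Amendment 2, so the commitment was current when v1.3 was finalised.

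**The case against.** The strongest reply is that little is lost.

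- **Creatinine.** Section 5.4.4 already summarises rises above 1 mg/dL from on-treatment values, and the eGFR < 30 half of the disputed table can be built. A reader might infer that none of about 1300 patients could ever be abnormal at the start. That is true only when the shift origin and the change reference are the same baseline, and v1.3 defines two without saying which applies. The ambiguity is itself a gap, and no patient results are shown to be wrong.
- **eGFR below 15.** Section 5.2.4 labels its classes as baseline classes and does not say that post-baseline columns stop there. A reader might infer that patients below 15 vanish from the renal output. They do not: 5.4.4 counts them, and renal AESI terms are tabulated. Nor did v1.3 delete a class that v1.0 had provided. The v1.0 clause on modifying post-baseline classes named values below 45 and below 30, not below 15.
- **Urine protein.** A reader might infer that proteinuria goes unanalysed. Listings remain, and the every-parameter abnormality counts in 5.4.4 could be read to include dipstick protein, although that conflicts with the listing-only sentence. That sentence alone does not prove removal, because v1.0 contained it beside an explicit urine-protein shift. The addendum, written against v1.2, lists the tables although v1.2 is silent on them.

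What stands is narrower. Section 4.5 defines the interim analyses by reference to the final one, so it does not bring an interim table into the final analysis. Version 1.3 has no table list of its own, and its text overrides the protocol. The shift is therefore not required at the final analysis, and 4.6 does not say so.

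**Conclusion.** The point holds at modest severity: one omitted analysis and two mis-specified tables.

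1. The final analysis has no specified urine-protein shift, contrary to Protocol 12.6, and the no-change statement in 4.6 is inaccurate on this item. This rests on v1.3 governing the final analysis, as its section 2 says.
2. The two-criterion shift table cannot work for creatinine when one baseline serves both purposes, and its two criteria are not levels of a single table.
3. The eGFR shift table has no stated column below 15. This assumes the 5.2.4 classes are the ones used, since v1.3 gives no others for a shift. The gap is confined to that table.

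The number of patients affected is unknown and cannot be derived from the documents. No inference or clinical threshold depends on these tables, but the corrections change what the final renal output shows.

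**What to change.** - **Urine protein.** Add the negative/positive shift table to 5.4.4.4 for the final analysis, exempt it from the listing-only sentence in 5.4.4, and say whether the every-parameter abnormality counts cover categorical urinalysis. Failing that, declare the removal in 4.6.
- **Two-criterion table.** Name the baseline. Rely on the post-baseline incidence of creatinine rise above 1 mg/dL already ordered in 5.4.4. Keep a yes/no shift, baseline against worst on-treatment value, for eGFR below 30 only.
- **eGFR shift.** State the post-baseline classes with contiguous cut-points: 90 and above, 60 to below 90, 30 to below 60, 15 to below 30, and below 15.

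The cost is a few SAP sentences and small programming changes on data already collected. The urine-protein tables are already in the Day 120 table list.

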#### 5.4.5 Physical Examination (PE)

Listings of PE data will include only those records where the body system at the baseline PE was normal, but the body system at a post-baseline PE was marked as 'Change from previous exam, clinically significant'. Baseline is defined as the last value prior to the first dose of study medication in OLE study. Only changes from baseline PE findings that meet the definition of an AE will be recorded on the AE page of the eCRF and will be summarized with other AE outcomes.

#### 5.4.6 Vital Signs and Weight

The observed values and changes from baseline of both parent study and OLE study in vital signs (heart rate, systolic blood pressure, diastolic blood pressure) and weight will be summarized using descriptive statistics by previous treatment group in parent study, overall and post-baseline time point.

Vital sign data will be listed for each patient, with increases from baseline of > 15 mmHg in systolic or diastolic blood pressure flagged.

## 6 DMC Analyses

Refer to DMC charter.

Confidential

Page 22 of 27

## 8 Appendices

Month	0	3	6	9	12	15	18/EOT 	19/EOS 
Week	EOS	Wk 12	Wk 24	Wk 36	Wk 52	Wk 64	Wk 78	Wk 82
	Parent							
Visit Window	30 Days	±7 days	+14 days					
	pre-M0							
In-clinic Visit	X	X			X		X	X
Phone Visit			Х	Х		Х		
Procedure			-	-		-		
Informed Consent	Х							
Enrollment Criteria	Х							
Medical History	Х							
Concomitant	Х	Х	Х	Х	Х	Х	Х	Х
Medications								
Adverse Event	Х	Х	Х	Х	Х	Х	Х	Х
Recording								
Physical Exam	Х				Х		Х	
Weight 	Х	Х			Х		Х	Х
Vital Signs 	Х	Х			Х		Х	Х
Urine Pregnancy Test 								
Clinical Safety Labs 	Х	Х			Х		Х	Х
Basic Fasting Lipids 	Х	Х			Х		Х	Х
Coagulation 	Х							
ApoB and hsCRP	Х	Х			Х		Х	Х
HbA 1C	Х				Х		Х	Х
IWRS Contact9	Х	Х			Х		Х	
Drug Dispensing	Х	Х			Х			
Drug Return/		Х			Х		Х	
Compliance	1 .1 1						6 11 1	

## 8.1 Appendix 1: Schedule of Events (Subject Visit Schedule)

NOTE: For patients who withdraw from study drug treatment, but consent to be followed for safety assessments and return to clinic for these visit, the visits will occur according to the protocol schedule. Safety assessments should include clinical safety and basic lipid laboratories, adverse events (AEs), physical examination (PE), and vital signs. For patients who withdraw from study drug treatment, but consent to be followed for safety assessments by phone, the telephone contacts will occur according the protocol schedule with information regarding current health status and to collect information on AEs (eg, recent procedures, hospitalizations, and if the patient has died, the cause of death). If a patient does not provide consent to be followed for safety assessments per the protocol (either by returning to clinic or by phone), Visit Week 78/End of Treatment (EOT) will be scheduled as soon as possible and the patient will be asked to come back 4 weeks after last investigational medicinal product (IMP) dose for Visit Week 82/End of Study (EOS). No further visits will be scheduled.

 All procedures will be completed for all patients at either EOT or early withdrawal.

 All procedures will be completed for all patients 4 weeks after last IMP dose if completing the study or early withdrawal.

 Body weight will be measured in the morning while fasting, using consistent scales, after voiding, and without shoes and outerwear (eg, coats).

 Vital signs will include diastolic blood pressure (DBP), systolic blood pressure (SBP), heart rate (HR) and will be collected prior to any blood sample collection. Patient will rest for 5 minutes prior to assessments

